4.4.2. BIC/FTC/TAF (BIK)

BIK will be administered as the marketed three-drug fixed dose combination product containing 50 mg of BIC, 200 mg of FTC, and 25 mg of TAF orally once daily with or without food in adults.

4.5. End of Study Definition

The investigator is responsible for ensuring that consideration has been given to the post-study care of the participant’s medical condition.

Study Completion

Participants are considered to have completed the study if they remain on therapy (i.e., have not permanently discontinued IP) and satisfy one of the following:

- Randomly assigned to either treatment group, completed the randomized Maintenance Phase including Month 11/12 (with or without Month 11/12 study treatment) and did not enter the Extension Phase;
- Randomly assigned to either treatment group, completed the randomized Maintenance Phase including Month 11/12, and entered and completed the Extension Phase (defined as remaining on study until commercial supplies of the CAB LA + RPV LA Q8W regimen become locally available or development of CAB LA + RPV LA is terminated).

An safety Follow-Up visit will be conducted approximately 4 weeks after the last dose of study medication for participants with ongoing AEs, and serious adverse events (SAEs) and also any laboratory abnormalities that are considered to be AEs or potentially harmful to the participant, at the last on-study visit. Assessments at the safety Follow-up visit should reflect any ongoing complaints (e.g., blood draws to follow a laboratory abnormality). Safety Follow-Up visits are not required for successful completion of the study and can be in clinic or conducted by phone.

5. STUDY POPULATION

Specific information regarding warnings, precautions, contraindications, adverse events, and other pertinent information on the investigational regimen or other study treatment that may impact participant eligibility is provided in the current IBs for CAB [GlaxoSmithKline Document Number [RPS-CLIN-004375](#), 2021 and [RPV IB](#), 2021], [Edurant](#) Prescribing Information, 2021 and [Biktarvy](#) prescribing information, 2019.

Deviations from inclusion and exclusion criteria are not allowed because they can potentially jeopardize the scientific integrity of the study, regulatory acceptability or participant safety. Therefore, adherence to the criteria as specified in the protocol is essential.

5.1. Inclusion Criteria

A participant will be eligible for inclusion in this study only if all of the following criteria apply:

- Be able to understand and comply with protocol requirements, instructions, and restrictions;
- Understand the long-term commitment to the study and be likely to complete the study as planned;
- Be considered appropriate candidates for participation in an investigative clinical trial with oral and intramuscularly injectable medications (e.g., no active substance use disorder, acute major organ disease, or planned long-term work assignments out of the country, etc.).

The following are study specific eligibility criteria unless stated otherwise. **In addition to these criteria, Investigators must exercise clinical discretion regarding selection of appropriate study participants, taking into consideration any local treatment practices or guidelines and good clinical practice (GCP). All participants must be considered appropriate candidates for antiretroviral therapy in accordance with local treatment guidelines.**

Laboratory results from the central laboratory services provided by this trial will be used to assess eligibility. In exceptional circumstances only, if a repeat lab is required because a central lab result cannot be generated, local labs can be reviewed and approved by the Medical Monitor for consideration of participant eligibility. A repeat central lab will be submitted concurrently or at the next planned visit.

Source documentation to verify entry criteria must be reviewed by the Principal Investigator or designee prior to randomization. Source documents from other medical facilities must be located/received during the 14-day screening phase (or up to 35 days) and under no circumstances may the participant be randomized in the absence of source documentation.

All Participants eligible for enrolment in the study must meet all of the following criteria:

AGE
1. Aged 18 years or older (or ≥ 19 where required by local regulatory agencies), at the time of signing the informed consent.
SEX

2. A female participant is eligible to participate if she is not pregnant (as confirmed by a negative serum human chorionic gonadotropin (hCG) test at screen and a negative urine hCG test at Randomization), not lactating, and at least one of the following conditions applies:
 
a. Non-reproductive potential defined as:
 
 • Pre-menopausal females with one of the following: 
 • Documented tubal ligation • Documented hysteroscopic tubal occlusion procedure with follow-up confirmation of bilateral tubal occlusion • Hysterectomy • Documented Bilateral Oophorectomy • Postmenopausal defined as 12 months of spontaneous amenorrhea [in questionable cases a blood sample with simultaneous follicle stimulating hormone (FSH) and estradiol levels consistent with menopause (refer to laboratory reference ranges for confirmatory levels)]. Females on hormone replacement therapy (HRT) and whose menopausal status is in doubt will be required to use one of the highly effective contraception methods if they wish to continue their HRT during the study. Otherwise, they must discontinue HRT to allow confirmation of post-menopausal status prior to study enrolment. 
b. Reproductive potential and agrees to follow one of the options listed in the Modified List of Highly Effective Methods for Avoiding Pregnancy in Females of Reproductive Potential (FRP) from 30 days prior to the first dose of study medication, throughout the study, for at least 30 days after discontinuation of all oral study medications, and for at least 52 weeks after discontinuation of CAB LA and RPV LA.

The investigator is responsible for ensuring that participants understand how to properly use these methods of contraception.

INFORMED CONSENT

3. Capable of giving signed informed consent, which includes compliance with the requirements and restrictions listed in the consent form and in this protocol. Eligible participants or their legal guardians (and next of kin when locally required), must sign a written Informed Consent Form before any protocol-specified assessments are conducted. Enrolment of participants who are unable to provide direct informed consent is optional and will be based on local legal/regulatory requirements and site feasibility to conduct protocol procedures.

OTHER

4. Participants enrolled in France must be affiliated to, or a beneficiary of, a social security category.
5. Must be on the uninterrupted current regimen of BIK for at least 6 months prior to Screening with an undetectable HIV-1 viral load for at least 6 months prior to Screening. BIK must be the participant's first or second regimen. If BIK is the second regimen, the first regimen must be an INI regimen. Any history of non-INSTI regimens (ie. NNRTI, PI, C-C chemokine receptor type 5 [CCR5] and other entry inhibitors) are not permitted. Any prior change in regimen, defined as a change of a single drug or multiple drugs simultaneously, must have occurred due to tolerability/safety, access to medications, or convenience/simplification, and must NOT have been done for treatment failure (HIV-1 RNA \geq 400 c/mL).

The following are limited exceptions:

- A change from TDF to TAF will not be considered a regimen change.
- Historical perinatal use of an NRTI when given in addition to an ongoing HAART will not be considered a change in ART regimen.
- The past use of ARVs in the context of PEP or PrEP while the patient was HIV negative will be allowed. Such cases will be evaluated on a case by case basis with the Medical Monitor, and may require documentation of HIV negative serology during time of PEP or PrEP
- A change in dosing scheme of the same drug from twice daily to once daily will not be considered a change in ART regimen if data support similar exposures and efficacy.
- A change in formulation from multiple class regimens to single treatment regimens (of the same medications) would not be considered a change in ART regimen.

- | |
|---|
| 
 6. Documented evidence of plasma HIV-1 RNA measurements <50 c/mL in the 6 months prior to Screening . 7. Plasma HIV-1 RNA <50 c/mL at Screening. |
|---|

All participants participating in the study should be counseled on safer sexual practices including the use and benefit/risk of effective barrier methods (e.g., male condom) and on the risk of HIV transmission to an uninfected partner.

5.2. Exclusion Criteria

Deviations from exclusion criteria are not allowed because they can potentially jeopardize the scientific integrity of the study, regulatory acceptability, or participant safety. Therefore, adherence to the criteria as specified in the protocol is essential. A participant will not be eligible for inclusion in this study if any of the following criteria apply:

Exclusionary Criteria prior to Screening or Day 1

 1. Within 6 months prior to Screening, any plasma HIV-1 RNA measurement ≥ 50 c/mL 2. Within the 6 to 12-month window prior to Screening, documented evidence of any plasma HIV-1 RNA measurement > 200 c/mL, or 2 or more plasma HIV-1 RNA measurements ≥ 50 c/mL. NOTE: This statement does not apply to study participants who started treatment within the 6 to 12-month window prior to screening. 3. History of prior treatment failure to any DHHS recommended ART regimen. 4. History of drug holiday > 1 month for any reason prior to Screening visit, except where all ART was stopped due to tolerability and/or safety concerns 5. Any change to a second line regimen, defined as change of a single drug or multiple drugs simultaneously, due to virologic failure to therapy (defined as a confirmed plasma HIV-1 RNA measurement ≥ 200 c/mL after initial suppression to < 50 c/mL while on first line HIV therapy regimen) 6. Participants who are currently participating in or anticipate being selected for any other interventional study.
Exclusionary medical conditions- for all participants

 7. Women who are pregnant, breastfeeding or plan to become pregnant or breastfeed during the study 8. Any evidence of a current Center for Disease Control and Prevention (CDC) Stage 3 disease [CDC, 2014], except cutaneous Kaposi’s sarcoma not requiring

systemic therapy, and CD4+ counts <200 cells/ μ L are not exclusionary.

9. Participants with moderate to severe hepatic impairment
10. Any pre-existing physical or mental condition (including substance use disorder) which, in the opinion of the Investigator, may interfere with the participant's ability to comply with the dosing schedule and/or protocol evaluations or which may compromise the safety of the participant
11. Participants determined by the Investigator to have a high risk of seizures, including participants with an unstable or poorly controlled seizure disorder. A participant with a prior history of seizure may be considered for enrolment if the Investigator believes the risk of seizure recurrence is low. All cases of prior seizure history should be discussed with the Medical Monitor prior to enrolment
12. All participants will be screened for syphilis.
 - Participants with untreated secondary (late latent) or tertiary syphilis infection, defined as a positive RPR and a positive treponemal test without clear documentation of treatment, are excluded.
 - Participants with a false positive RPR (with negative treponemal test) or serofast RPR result (persistence of a reactive nontreponemal syphilis test despite history of adequate therapy and no evidence of re-exposure) may enroll after consultation with the Medical Monitor.
 - Participants with primary syphilis or early latent secondary syphilis (acquired within the preceding year) who have a positive RPR test and have not been treated may be treated during the screening period and if completion of antibiotic treatment occurs during the screening period, may be allowed entry after consultation with the Medical Monitor. If antibiotic treatment cannot be completed before the screening window ends, participants may be rescreened once following completion of antibiotic therapy for primary or early latent secondary syphilis.
13. Participants who, in the investigator's judgment, pose a significant suicide risk. Participant's recent history of suicidal behavior and/or suicidal ideation should be considered when evaluating for suicide risk
14. The participant has a tattoo, gluteal implant/enhancements or other dermatological condition overlying the gluteus region which may interfere with interpretation of injection site reactions
15. Evidence of Hepatitis B virus (HBV) infection based on the results of testing at Screening for Hepatitis B surface antigen (HBsAg), Hepatitis B core antibody (anti-HBc), Hepatitis B surface antibody (anti-HBs) and HBV DNA as follows:
 - a. Participants positive for HBsAg are excluded;
 - b. Participants negative for anti-HBs but positive for anti-HBc (negative HBsAg status), whether negative or positive for HBV DNA, are excluded

Note: Participants positive for anti-HBc (negative HBsAg status) and positive for anti-HBs (past and/or current evidence) are immune to HBV and are not excluded.

16. Asymptomatic individuals with chronic hepatitis C virus (HCV) infection will not be excluded, however Investigators must carefully assess if therapy specific for HCV infection is required; participants who require or qualify for immediate HCV treatment are excluded (see Section 5.3.1 for those co-infected participants who post entry into SOLAR decide treatment for HCV infection is warranted or desired either by the participant or by the treating physician).

Participants with HCV co-infection will be allowed entry into this study if:

- a. Liver enzymes meet entry criteria
- b. HCV Disease has undergone appropriate work-up, and is not advanced, and will not require treatment prior to the Month 14 visit. Additional information (where available) on participants with HCV co-infection at screening should include results from any liver biopsy, Fibroscan, ultrasound, or other fibrosis evaluation, history of cirrhosis or other decompensated liver disease, prior treatment, and timing/plan for HCV treatment.
- c. In the event that recent biopsy or imaging data is not available or inconclusive, the Fib-4 score will be used to verify eligibility
 - i. Fib-4 score >3.25 is exclusionary
 - ii. Fib-4 scores 1.45 – 3.25 requires Medical Monitor consultation

Fibrosis 4 Score Formula:

$$(\text{Age} \times \text{AST}) / (\text{Platelets} \times (\text{sqr} [\text{ALT}]))$$

17. Unstable liver disease (as defined by any of the following: presence of ascites, encephalopathy, coagulopathy, hypoalbuminemia, esophageal or gastric varices, or persistent jaundice or cirrhosis, or decompensated cirrhosis (eg. ascites, encephalopathy, or variceal bleeding)), known biliary abnormalities (with the exception of Gilbert's syndrome or asymptomatic gallstones or otherwise stable chronic liver disease per investigator assessment)

18. History of liver cirrhosis with or without hepatitis viral co-infection.

19. Ongoing or clinically relevant pancreatitis

20. Clinically significant cardiovascular disease, as defined by history/evidence of congestive heart failure, symptomatic arrhythmia, angina/ischemia, coronary artery bypass grafting (CABG) surgery or percutaneous transluminal coronary angioplasty (PTCA) or any clinically significant cardiac disease

21. Ongoing malignancy other than cutaneous Kaposi's sarcoma, basal cell carcinoma, or resected, non-invasive cutaneous squamous cell carcinoma, or cervical intraepithelial neoplasia; other localized malignancies require agreement between the investigator and the Study medical monitor for inclusion of the participant prior to randomization

22. Any condition which, in the opinion of the Investigator, may interfere with the absorption, distribution, metabolism or excretion of the study drugs or render the participant unable to receive study medication

23. History or presence of allergy or intolerance to the study drugs or their components or drugs of their class. In addition, if heparin is used during PK sampling, participants with a history of sensitivity to heparin or heparin-induced thrombocytopenia must not be enrolled
24. Current or anticipated need for chronic anti-coagulation with the exception of the use of low dose acetylsalicylic acid (≤ 325 mg) or hereditary coagulation and platelet disorders such as haemophilia or Von Willebrand Disease.
25. Corrected QT interval (QTc (Bazett)) >450 msec or QTc (Bazett) >480 msec for participants with bundle branch block.
26. Known or suspected active COVID-19 infection OR has had contact with an individual with known COVID-19, within 14 days of study enrolment.

Exclusionary Laboratory Values or Clinical Assessments at Screening (a single repeat to determine eligibility is allowed)

27. Known or suspected presence of resistance mutations as defined by the IAS-USA resistance guidelines [IAS-USA, 2019] to the individual components of BIK (BIC, FTC, TAF), RPV, and CAB by any historical resistance test result.

Note: Prior genotypic resistance testing (genotyping of plasma vRNA and/or PBMC vDNA) is not required but if available it must be provided to ViiV, after screening and before randomization according to guidance in the SPM, to provide direct evidence of no pre-existing exclusionary resistance mutations. You must wait for the study virologists to confirm the lack of exclusionary resistance mutations, which will be provided before the screening window closes. Details regarding baseline or prior resistance data must be noted in the source documentation
28. Any verified Grade 4 laboratory abnormality. A single repeat test is allowed during the Screening phase to verify a result
29. Any acute laboratory abnormality at Screening, which, in the opinion of the investigator, would preclude the participant's participation in the study of an investigational compound
30. Participant has estimated creatine clearance <30 mL/min per 1.73m^2 via Chronic Kidney Disease-Epidemiology Collaboration (CKD-EPI) Method
31. Alanine aminotransferase (ALT) $\geq 3 \times$ ULN

Concomitant Medications

32. Exposure to an experimental drug or experimental vaccine within either 30 days, 5 half-lives of the test agent, or twice the duration of the biological effect of the test agent, whichever is longer, prior to Day 1 of this study;
 
33. Treatment with any of the following agents within 28 days of Screening:
 
 • radiation therapy; • cytotoxic chemotherapeutic agents; • tuberculosis therapy with the exception of isoniazid (isonicotinylhydrazid, INH); • anti-coagulation agents; • Immunomodulators that alter immune responses such as chronic systemic corticosteroids, interleukins, or interferons. Note: Participants using short-term (e.g. ≤ 21 days) systemic corticosteroid treatment; topical, inhaled and intranasal corticosteroids are eligible for enrolment. 
34. Treatment with an HIV-1 immunotherapeutic vaccine within 90 days of Screening
 
35. Treatment with any agent, except recognized ART as allowed above, with documented activity against HIV-1 within 28 days of study Day 1. Treatment with acyclovir/valacyclovir is permitted.
 
36. Use of medications which are associated with Torsade de Pointes. (See SPM for a list of relevant medications)
 
37. Participants receiving any prohibited medication and who are unwilling or unable to switch to an alternate medication. Note: Any prohibited medications that decrease CAB, RPV, BIC, FTC or TAF concentrations should be discontinued for a minimum of four weeks or a minimum of three half-lives (whichever is longer) prior to the first dose and any other prohibited medications should be discontinued for a minimum of two weeks or a minimum of three half-lives (whichever is longer) prior to the first dose

5.3. Additional Eligibility Criteria

To assess any potential impact on participant eligibility with regard to safety, the investigator must refer to the IB and supplements, approved product labels, and/or local prescribing information for detailed information regarding warnings, precautions, contraindications, AEs, drug interactions, and other significant data pertaining to the study drugs.

Notwithstanding these minimum inclusion and exclusion criteria, investigators must also follow country specific guidelines where they exist when making decisions about participants who are eligible for study participation.

5.3.1. HIV/HCV Treatment Considerations for Co-infected Participants

For participants who decide to initiate HCV treatment at any point while on study, either secondary to newly acquired acute HCV infection or, if a change in treatment strategy for those who entered the study HIV/HCV co-infected, such participants may be permitted during the Maintenance Phase before the primary endpoint is reached but would require consultation with and approval by the Medical Monitor to commence HCV therapy. The choice of HCV direct acting antiviral agents being considered must be HCV regimens endorsed by DHHS guidelines with minimal drug-drug interactions as detailed in the most current DHHS HIV treatment guidelines.

5.4. Screening/Baseline/Run-in Failures

Screen failures are defined as participants who consent to participate in the clinical trial but are never subsequently randomized. In order to ensure transparent reporting of screen failure participants, meet the Consolidated Standards of Reporting Trials (CONSORT) publishing requirements, and respond to queries from Regulatory authorities, a minimal set of screen failure information is required including Demography, Screen Failure details, Eligibility Criteria, and Serious Adverse Events.

A single repeat of a procedure / lab parameter is allowed to determine eligibility (unless otherwise specified).

Participants are allowed to re-screen for this study one time. This will require a new participant number.

5.5. Lifestyle Considerations

5.5.1. Meals and Dietary Restrictions

Participants who are randomized to the CAB + RPV arm and choose to participate in the oral lead in should take the recommended dosage of oral CAB 30 mg + RPV 25 mg once daily with a meal. Co-administration of antacid supplements has the potential to decrease oral cabotegravir absorption and has not been studied. Antacid products containing polyvalent cations are recommended to be administered at least 2 hours before or 4 hours after oral CAB.

If the participant is randomized to BIK and calcium-containing supplements can be taken together, without regard to food. BIK should be administered at least 2 hours before iron supplements or taken together with food. BIK should be administered at least 2 hours before, or with food 2 hours after antacids containing magnesium and/or aluminium.

5.5.2. Cosmetic Surgery

Participants who are randomised to the BIK or CAB +RPV arm will be questioned at the end of the study if they had any cosmetic surgery during the course of the study only. Cosmetic procedures such as liposuction/liposculpture/implants (but not limited to) may affect metabolic endpoints CCI

CCI Therefore, such patients will be excluded from the final analyses for these

metabolic endpoints. Cosmetic procedures involving the face and neck are out of scope as such procedures are unlikely to have an impact on these metabolic endpoints.

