- z. Participants receiving one or more injections with CAB LA and/or RPV LA will be assessed with clinic visits at Months 3, 6, 9 and 12 during the Long-Term Follow-Up Phase
- aa. BIK dispensation (1-month supply) for participants who plan on entering into the Extension Phase. Participants who do not enter the Extension Phase or do not wish to transition to the commercial supply will not receive 1-month supply at M12.
- bb. Data from visit will be used to determine participant's eligibility to enter the Extension Phase of study. If participant elects to enter the Extension Phase, determine if the participant will elect to start injections immediately or start with oral lead in.
- cc. All PROs are recommended to be administered before other assessments and injections take place at each designated visit.
- dd. Only collected if Withdrawal visit occurs during the Maintenance Phase.
- ee. Will be administered only to participants randomized to BIK, successfully completing the Maintenance Phase and deciding to enter Extension Phase and switching to CAB LA + RPV LA.
- ff. When assessing CDC stage at Screening/Baseline, consider only the latest available CD4 T-cell count, except when the participant had an active Stage 3 event 6 months prior to Screening.
- gg. At Month 11 (D2I)/ Month 12 (OLI or BIK) or withdrawal, (depending which is sooner) participants will be asked if any cosmetic procedures were performed during the conduct of the study.

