2.1.2. Weight Gain

Weight gain in people living with HIV is multifactorial with both traditional (diet, exercise, concomitant medications such as selective serotonin reuptake inhibitor and others) and HIV specific modifiable risks likely contributing factors. Which factor or factors are most significant in the pathogenesis of weight gain in HIV disease has not been fully elucidated.

Whereas lipodystrophy involved accumulation of central abdominal or visceral fat, and loss of subcutaneous fat, weight gain in HIV-infected individuals receiving newer, more recently approved antiretroviral treatment consists of general fat gain – both subcutaneous and central fat – with an increase in waist circumference. Weight gain among HIV-infected individuals often occurs after the initiation of antiretroviral therapy with certain antiretrovirals linked more closely to weight gain than others. Teasing out what is considered appropriate weight gain for individuals returning back to health versus what is considered more pathogenic weight gain has been challenging. Recent studies have demonstrated increase weight gain with integrase strand transfer inhibitor (INSTI)-based regimens compared to other classes of antiretroviral therapy [Bourgi, 2019; Kerchberger, 2019; McComsey, 2019]. Moreover, additional components of the antiretroviral regimen,

specifically the nucleoside reverse transcriptase inhibitor TAF has also been associated with excess weight gain [McCann, 2019]. Women and non-whites appear to be most at risk.

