3. OBJECTIVES AND ENDPOINTS

Objectives	Endpoints
Primary	
To demonstrate the non-inferior antiviral activity of CAB LA + RPV LA every two months compared to a BIK single tablet regimen administered once daily over 12 months in suppressed HIV-1 infected antiretroviral therapy (ART)-experienced participants	Proportion of participants with plasma HIV-RNA greater than or equal to 50 copies/mL as per Food and Drug Administration (FDA) Snapshot algorithm at Month 12 (OLI and BIK)/Month 11 (D2I) (Intent-to-Treat Exposed [ITT-E] population)
Secondary	
To demonstrate the antiviral and immunologic response with the use of CAB LA + RPV LA every 2 months compared to a BIK single tablet regimen administered once daily	Proportion of participants with plasma HIV-1 RNA <50 c/mL (c/mL) at Month 6 and Month 12 (OLI and BIK)/Month 5 and Month 11 (D2I) using the FDA Snapshot algorithm (Intent-to-Treat Exposed [ITT-E] population)

Objectives	Endpoints
	
Proportion of participants with protocol-defined confirmed virologic failure (CVF) through Month 6 and Month 12 (OLI and BIK)/Month 5 and Month 11 (D2I).
 
Proportion of participants with HIV-RNA greater than or equal to 50 c/mL as per FDA Snapshot algorithm at Month 6, and Month 12 (OLI and BIK)/Month 5 and Month 11 (D2I)
 
Absolute values and changes from Baseline in viral load and CD4+ cell count over time including Month 6 and Month 12 (OLI and BIK)/Month 5 and Month 11 (D2I)

To assess viral resistance in participants experiencing protocol-defined confirmed virologic failure	Incidence of treatment emergent genotypic and phenotypic resistance to CAB, RPV, BIC, FTC, and TAF through Month 6 and Month 12 (OLI and BIK)/Month 5 and Month 11 (D2I).
To evaluate renal (in urine and blood) and bone (in blood) biomarkers in participants treated with CAB LA + RPV LA compared to BIK	Change from Baseline (Day 1) in renal and bone biomarkers at Months 6 and 12 (OLI and BIK)/Month 5 and Month 11 (D2I).
To evaluate Metabolic Syndrome for participants treated with CAB + RPV and BIK	Change from Baseline in proportions of participants with Metabolic syndrome at Months 6 and 12 (OLI and BIK)/Month 5 and Month 11 (D2I)
To evaluate insulin resistance in participants treated with CAB LA + RPV LA compared to BIK	Change from Baseline (Day 1) in homeostasis model of assessment-insulin resistance (HOMA-IR) at Months 6 and 12 (OLI and BIK)/Month 5 and Month 11 (D2I).

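### Section 5.5.2 drops whole participants from the metabolic analyses for a body cosmetic procedure after randomization, including values recorded before it

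*Protocol*

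**What the plan says.** Protocol section 5.5.2 applies to both arms. Participants are questioned at the end of the study about whether "if they had any cosmetic surgery during the course of the study only". The reason given is that "Cosmetic procedures such as liposuction/liposculpture/implants (but not limited to) may affect metabolic endpoints"; a redaction follows. The consequence is that "such patients will be excluded from the final analyses for these" metabolic endpoints. One carve-out is made: "Cosmetic procedures involving the face and neck are out of scope". The rule names patients. It does not limit itself to values after the procedure, and it is presented as the analysis rather than as a sensitivity analysis.

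Footnote gg of the Schedule of Activities (section 1.3) sets the ascertainment. At Month 11 (D2I) or Month 12 (OLI, BIK), or at withdrawal if sooner, "participants will be asked if any cosmetic procedures were performed during the conduct of the study". The footnote mentions no date or body site.

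The visible metabolic endpoints in section 3 include "Change from Baseline in proportions of participants with Metabolic syndrome" at Months 6 and 12 (5 and 11 for D2I), and HOMA-IR at the same visits. Table 1 in section 2.1.2 builds metabolic syndrome from waist circumference, triglycerides, HDL cholesterol, blood pressure and fasting glucose.

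On mechanism, section 2.1.2 says of a BIK component that "TAF has also been associated with excess weight gain", and describes gain on newer antiretrovirals as general fat gain, "both subcutaneous and central fat". Section 6.3.2 confirms that the trial is open label.

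**The concern.** A cosmetic procedure during the study is a post-randomization event. If its frequency, or the kind of person who has it, differs by arm, removing those people leaves two groups that randomization no longer makes comparable. The protocol supplies a reason to take this seriously. It regards a between-regimen difference in weight and fat as an open study question, and participants know which regimen they are on. Someone who gains fat and then has liposuction would be removed partly because of the outcome being studied.

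The rule also costs data for no gain. A participant with a procedure at Month 10 would lose Day 1 and Month 5/6 values that the procedure cannot have touched. At stake is the comparison of metabolic secondary endpoints, not the non-inferiority conclusion.

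**Working it through.** **1. No plan figure to reproduce.** The protocol attaches no number to this rule and gives no procedure rate. Everything numerical below is illustration on assumed inputs.

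**2. What is discarded.** By the Schedule of Activities, waist is measured on Day 1 and at Months 2, 4, 6 and 12 in OLI and BIK participants (Day 1 and Months 1, 3, 5 and 11 in D2I). Fasting glucose and lipids are taken on Day 1 and at Months 6 and 12 (5 and 11). For a Month 10 procedure, only the last of these visits follows it. Section 5.5.2 nevertheless removes the participant from the final analyses. By contrast, section 7.1 keeps a withdrawn participant's efficacy data evaluable up to withdrawal and includes safety data from everyone who received study drug. Section 9.3.1 defines ITT-E as all randomized and dosed participants.

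**3. Ascertainment.** The question is asked once, retrospectively. A participant lost to follow-up (section 7.2) cannot answer it and so keeps any earlier values in the analysis, while a completer with the same procedure is removed.

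**4. Size, metabolic-syndrome prevalence.** Let p be an arm's true prevalence, f the share excluded and r the prevalence among those excluded. Prevalence in those retained is (p − f·r)/(1 − f), so the shift in one arm is −f(r − p)/(1 − f). Assume p = 25% in both arms, so the true difference is 0.

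| Excluded, CAB LA + RPV LA / BIK | r | Retained, CAB LA + RPV LA | Retained, BIK | Apparent difference (points) |
|---|---|---|---|---|
| 1% / 1% | 50% | 24.747% | 24.747% | 0.00 |
| 1% / 3% | 50% | 24.747% | 24.227% | +0.52 |
| 1% / 3% | 80% | 24.444% | 23.299% | +1.15 |
| 1% / 5% | 50% | 24.747% | 23.684% | +1.06 |
| 1% / 5% | 80% | 24.444% | 22.105% | +2.34 |

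Example, last row: (0.25 − 0.01×0.80)/0.99 = 0.24444 and (0.25 − 0.05×0.80)/0.95 = 0.22105; the difference is 0.0234.

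**5. With a true difference.** Take 22% versus 28% (−6.0 points) with 1% and 5% excluded. At r = 50%: 0.215/0.99 − 0.255/0.95 = 21.717% − 26.842% = −5.12 points. At r = 80%: 0.212/0.99 − 0.240/0.95 = 21.414% − 25.263% = −3.85 points.

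**6. Scale.** With the planned 436 and 218 participants (Table 7), 1% of 436 is 4.4 people, 3% of 218 is 6.5 and 5% of 218 is 10.9. At 25% prevalence the standard error of the difference is √[0.25×0.75×(1/436 + 1/218)] = 0.036, or 3.6 points. The illustrated shifts are therefore smaller than one standard error.

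**The case against.** The sponsor has a real problem to solve. Liposuction or implants change waist, hip and weight directly, and keeping later values untouched would distort the measurements. The exclusion is prespecified, applies equally to both arms and leaves out face and neck procedures. The protocol states no margin, hypothesis or alpha for the metabolic endpoints. All of this stands. It supports special handling of affected later values, but not deletion of the whole participant.

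Several stronger readings are tempting and are not supported:

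- **That the bias favours the regimen causing more fat gain.** This requires procedures to follow fat gain. The rule also names implants, which need not. The sign depends on r − p and on which arm has more exclusions, and the protocol gives neither.
- **That gluteal injections would deter gluteal procedures in one arm.** The gluteal-implant criterion in section 5.2 is an entry criterion for all participants. Neither it nor section 5.5.2 sets an arm-specific rule during the study.
- **That prevalence could move by the full share removed, such as 3 points for 3%.** At an assumed prevalence of 25%, even if every excluded person has metabolic syndrome, the shift is 0.03×0.75/0.97 = 2.3 points.
- **That a weight-change endpoint is distorted.** None is visible in section 3. Weight appears in the rationale and as a measurement.
- **That laboratory endpoints such as HOMA-IR are certainly covered.** This is plausible, but redaction hides part of the endpoint description.
- **That the Month 6 interim analysis is affected.** The rule speaks of final analyses, and the question is asked at Month 11/12 or withdrawal. Whether it reaches the interim is open.

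**Conclusion.** The point holds in a limited form. Section 5.5.2 fixes a whole-participant exclusion on a post-randomization event that may depend on treatment and on fat gain, and it discards values from before that event. This is a stated rule, not something left open: a statistical analysis plan that follows the protocol inherits it.

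The consequence is confined to metabolic secondary endpoints. The primary endpoint, its power and the key secondary endpoint (the proportion with HIV-1 RNA below 50 c/mL) are unaffected. The number of participants is unknown and probably small. Dependence on treatment is plausible but not shown.

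Under the assumptions in the working, the spurious difference in metabolic-syndrome prevalence runs from about 0.5 to 2.3 points when 1% is excluded in one arm and 3% to 5% in the other. With no true difference it is zero when the share and kind excluded match across arms. These inputs are assumptions, and real values could lie outside them. It is worth correcting because the correction is cheap and keeps the sponsor's purpose.

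**What to change.** Amend section 5.5.2 as follows:

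- Keep all ITT-E/Safety participants in the metabolic analyses.
- Record the type, body site and date of each procedure, if the eCRF does not already do so.
- Keep every value from before the procedure.
- After the procedure, set only directly affected measurements (for example waist, hip, weight) to missing, and retain blood-pressure and laboratory components.
- Name the missing-data method. The protocol shows no model for these endpoints, and section 9.4.2 makes observed-case data primary for safety endpoints. Under observed-case summaries, setting values to missing would drop the same people again at Month 11/12.
- Report the number of procedures by arm.
- Give two sensitivity analyses: all values used regardless of surgery, and the current full exclusion.

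The cost is a protocol wording change, possibly a date and site field on an existing question, and a few values handled by the missing-data method.
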